## 4.2 Analysis Populations

Two analysis sets are defined for the booster sub-study.

### 4.2.1 Booster Full Analysis Set (BFAS)

This is the subset of subjects who received a booster dose of MVA-BN-RSV vaccine and for whom any post-booster data are available.

### 4.2.2 Booster Immunogenicity Analysis Set (BIAS)

This is the subset of subjects in the BFAS who were from the PBMC subgroup.

Additional analysis sets may need to be defined during the data review meeting and would be described in the clinical study report.

## 4.3 Data Handling Conventions

### 4.3.1 Missing Immunogenicity Data

Analysis of immunogenicity variables will be done on a valid case basis, i.e. for missing observations, no imputation technique such as “last observation carried forward” will be applied, since this could introduce an optimistic bias into the analysis.

For assay results that are below the detection limit, refer to Appendix [6.1](#).

### 4.3.2 Missing or Partial Dates in Adverse Event and Concomitant Medication Data

In the case of incomplete AE and/or medication start and end dates, the following rules will be used to assign AEs to the vaccination period and medications as prior/concomitant:

For analysis purposes of any Prior and Concomitant Medication or any AE, imputation of partial start and end dates will be performed based on the following rules:

| Missing            | Rule for start date | Rule for end date    | Flag for imputation |
|--------------------|---------------------|----------------------|---------------------|
| Day                | First day of month  | Last day of month    | D                   |
| Month † | January 1           | December 31          | M                   |
| Year †  | Vaccination date    | Last BATP visit date | Y                   |

† It is assumed that a missing month implies a missing day as well, and that a missing year implies a missing month and day.

#### Partial/Missing Start Date

- If day is missing, then impute the 1st of the month as in the table above, but if the month is the same as the month of the booster vaccination date then assign the imputed start date as the vaccination date.

---

- If month and day are missing, then impute as above to January 1 unless the year is the same as for the vaccination date then assign imputed start date as the vaccination date.
- If the date is completely missing, then impute the vaccination date unless the end date indicates that the AE/medication could have started/been taken prior to this in which case the date is imputed to January 1 of the same year as the start date.

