### Booster Visit 0 (Days -28 to -1)

#### The following tasks will be performed:

- Subject to read, sign and date ICF and HIPAA
- Check Inclusion/Exclusion criteria for booster substudy
- Recording of SAEs since last FU visit in main trial

Booster Visit 0 (Days -28 to -1)

• Complete physical examination including auscultation of heart and lungs and measurement of body weight

• Evaluation of vital signs

• Recording of prior and concomitant medication

• Counseling on avoidance of pregnancy: Review of acceptable contraceptive methods and recent menstrual history with WOCBP

• Recording of AEs/SAEs after ICF signature

• Blood draw for safety laboratory 11 mL including

○ Hematology & serum chemistry

Additional safety measures (which may include troponin testing, ECG, etc.) can be taken at this or at any other trial visit or at unscheduled visits, if clinically indicated.

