#### Partial/Missing Start Date

- If day is missing, then impute the 1st of the month as in the table above, but if the month is the same as the month of the first vaccination date then assign the imputed start date as the first vaccination date.
- If month and day are missing, then impute as above to January 1 unless the year is the same as the first vaccination date then assign imputed start date as the first vaccination date.
- If the date is completely missing, then impute the first vaccination date unless the end date indicates that the AE/medication could have started/been taken prior to this in which case the date is imputed to 1st January of the same year as the start date.

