#### **4.3.3 Assignment of AEs to Trial Phase**

Each AE will be assigned to the booster active trial phase (BATP) or booster follow-up (BFU) phase using date/time of vaccination and date/time of onset of the AE:

- All AEs starting at or after the booster vaccination but before the BEAP visit will be assigned to the booster active trial phase. For subjects who missed the BEAP visit, AEs within the booster vaccination + 28 day will also be assigned to the BATP.
- Any AEs starting after the booster vaccination but are not assigned to the BATP belong to the BFU period.

If onset time is missing and start date of AE coincides with the date of vaccination, the AE will be assigned to the BATP.

Each AE starting on or after the booster vaccination not matching the definition of a solicited AE is defined as an unsolicited AE. If a solicited AE begins outside of the 8-day period following the booster vaccination it will be considered an unsolicited AE regardless of the preferred term (PT). If start time of the AE is missing and start date coincides with date of vaccination, it will be

---

regarded as a treatment-emergent AE. If the start date is (partially) missing the AE will be regarded as a treatment-emergent AE following the worst-case principle.

Worst-case principle:

To avoid a potential misclassification of an AE to the BATP, if an imputed start date corresponds to the first of the month or to the first of the year, and matches the month and year of the booster vaccination date, then the AE will be assigned to the BATP. If the AE cannot be assigned to either phase because of a (partially) missing start date then it will be assigned to the BATP.

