##### **Medical History**

A summary of medical history by System Organ Class (SOC) and PT per MedDRA 19.1 will be produced by treatment group for the BFAS. A medical history listing will be presented for the BFAS.

Medical history refers to disease or symptoms presented prior to first MVA-BN-RSV vaccination in the main study. Any SAEs since the last follow-up visit in the main study will be listed separately.

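### Two of the booster SAP's three start-date imputation rules ignore the end date, so an event that ended before the booster can be re-dated to booster day, and nothing says which section governs events recorded before the injection

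*SAP*

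**What the plan says.** Booster SAP 4.3.2 (Partial/Missing Start Date) has three rules.

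- Day missing: impute the first of the month, "but if the month is the same as the month of the booster vaccination date then assign the imputed start date as the vaccination date".
- Month and day missing: impute 1 January, "unless the year is the same as for the vaccination date then assign imputed start date as the vaccination date".
- Wholly missing: impute the booster date, with one exception, which does consult the end date: "unless the end date indicates that the AE/medication could have started/been taken prior to this". The substitute date under this exception is worded separately: "in which case the date is imputed to January 1 of the same year as the start date".

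Section 4.3.2 then says that imputed dates decide which period an event belongs to, while listings keep the dates as entered. Section 4.3.3 puts any start from the booster until the BEAP visit into the booster active trial phase, and adds: "If the start date is (partially) missing the AE will be regarded as a treatment-emergent AE following the worst-case principle". Section 4.5.8 tabulates SAEs with onset from the booster to BEAP.

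On events that precede the injection, Protocol 4.2.2.1 schedules at BV0 (Days -28 to -1): "Recording of SAEs since last FU visit in main trial". Booster SAP 4.5.4 (Medical History) says: "Any SAEs since the last follow-up visit in the main study will be listed separately". The pre-treatment paragraph of 4.5.8 goes by time of recording: anything entered between booster consent and the injection is pre-treatment and is listed. Listing 16.2.4.1.3 covers both kinds of event.

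Main SAP 3.3.2 has the same three start-date rules, tied to the first vaccination. Its third ends: "in which case the date is imputed to 1st January of the same year as the start date".

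**The concern.** Imputing toward the vaccination date is a conventional conservative choice when the order of event and injection is unknown. It is not conservative when the recorded end date already shows that the event was over before the injection. In that case the rule contradicts a recorded date and creates a booster event that did not occur. The authors saw the need for an end-date check, because the third rule has one; the first two do not.

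The second problem is a conflict between sections. Events collected at BV0, or before dosing at BV1, precede the booster by design. Sections 4.5.4 and 4.5.8 intend to keep them apart, but 4.3.3 labels any partial start treatment-emergent, offers only the active and follow-up phases, and sends unassignable events to the active phase. A programmer who follows 4.3.2 and 4.3.3 literally gets a different answer from one who starts from the pre-treatment paragraph.

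At stake are the SAE and TEAE counts after the booster, which serve a stated secondary objective and are tabulated by dose group with about 43 subjects each.

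**Working it through.** The plan states no figure on this point, so there is none to reproduce. The check is a trace of the rules, followed by an illustration of how far each one reaches.

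**Trace.** Hypothetical subject: BV0 on 20 March, booster on 25 March of the same year.

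| Start as recorded | End | Imputed start | Result |
|---|---|---|---|
| March, day missing | 15 March | 25 March | Start after its own end; active-phase event |
| Year only, same year | 20 January | 25 March | Start after its own end; active-phase event |
| February, day missing | 28 February | 1 February | Not moved, though the 4.3.3 sentence on partial dates, read alone, still calls it treatment-emergent |
| Wholly missing | 20 January | 1 January | Not moved, because the end date is checked |

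The last row works only if the year is taken from the end date; as worded, the rule points to the start date, which is absent. Two of the four events become booster events. With an end-date check in the first two rules, neither does.

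The pre-treatment paragraph could rescue the first two rows if they were recorded at BV0. It could not if the same event was first mentioned after the booster, for example at BV2. Then only an end-date check keeps it out.

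**Reach of each rule.** Inputs from the protocol schedules: V3 at day 28–35; FU2 at V3 + 182–210 days; BV1 about 11–13 months after first vaccination; BV0 1–28 days before BV1.

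- FU2 falls at day 28 + 182 = 210 to 35 + 210 = 245.
- BV1 falls at 11 × 30.4375 ≈ 335 to 13 × 30.4375 ≈ 396.
- The FU2-to-BV0 gap runs from 335 − 28 − 245 = 62 to 396 − 1 − 210 = 185 days.

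Assumptions: onset is uniform over the gap, booster dates are spread evenly over a calendar year, and a matching month means the same month of the same year. The share re-dated is the number of (booster date, onset date) pairs in the same month, or year, divided by all pairs.

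| Gap (days) | BV0 to BV1 (days) | Day missing | Year only |
|---|---|---|---|
| 62 | 1 | 0.237 | 0.914 |
| 62 | 14 | 0.076 | 0.878 |
| 62 | 28 | 0.002 | 0.840 |
| 120 | 1 | 0.123 | 0.834 |
| 120 | 14 | 0.039 | 0.799 |
| 120 | 28 | 0.001 | 0.760 |
| 185 | 1 | 0.080 | 0.745 |
| 185 | 14 | 0.025 | 0.710 |
| 185 | 28 | 0.001 | 0.671 |

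Among onsets before BV0, the date rule alone moves about 0.1% to 24% of those with a missing day and about 67% to 91% of those with only a year. These shares are conditional on the date being partial and ignore the pre-treatment paragraph. They are not event counts.

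**Size of one error.** Planned group size is 43 (booster SAP 4.1): 1/43 = 0.023, or 2.3 percentage points on a group's SAE rate.

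**The case against.** A reader might infer that SAEs reported at BV0 will be counted as booster SAEs and produce a false safety signal. The documents do not support that. The pre-treatment paragraph classifies by recording time, BV0 recording follows the new consent and precedes the injection, and gap SAEs have their own listing. For these events the defect is an unresolved conflict, not a settled misclassification. Part of this answer remains open: listing an event separately does not by itself remove it from the tables, and no section says which text prevails.

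A reader might also assume that recall at BV0 makes partial SAE dates common. Nothing in the documents shows this. Protocol 8.3.1 includes onset date in the minimum content of an initial SAE report, and Protocol 9.3.2 has each SAE described individually. Year-only dates, the one wide route, are least plausible for SAEs. Applying an assumed SAE rate to the gap would count gap SAEs, not re-dated ones.

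The worst-case principle is deliberate and reasonable where the order is unknown, and its definition in 4.3.3 is narrower than the sentence on partial dates. That stands, but does not cover an event whose end date settles the order. Listings show the dates as entered, so a reviewer could notice a start after its end; the tables would still carry the error. The year reference in the third rule is an editorial slip with an obvious reading, and in the main SAP the BV0 recall period does not arise. Both reduce the weight of those items without making the wording correct.

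**Conclusion.** Wrong as written, minor severity. The day-missing and year-only rules can give an event a start after its recorded end and count it as a booster event, including in the SAE table if serious. That follows from the text and needs no assumption. For events recorded before the injection, the supportable conclusion is that the sections conflict and precedence must be stated; it is not that such events will be miscounted. The year reference in the third rule, in both SAPs, is a wording error.

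The number of affected events is unknown, because no frequency of partial dates is given, and is probably small. The shares above rest on uniform onset and evenly spread booster dates. The 2.3 percentage points is the effect of a single misplaced SAE in a group of 43, not an expected bias.

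**What to change.** 1. Booster SAP 4.3.2, first and second start-date rules: do not impute the booster date if the end date is before the booster; keep the onset pre-booster.
2. Booster SAP 4.3.3: state that events classed as pre-treatment under 4.5.8, and SAEs from the gap under 4.5.4, keep that status whatever start is imputed. State that the worst-case rule applies only when the known part of the start date, the end date and the recording visit all leave onset on or after the booster possible.
3. Booster SAP 4.3.2, third rule: take the year from the end date instead of the start date.
4. Main SAP 3.3.2: add the same end-date check to the first two rules, relative to the first vaccination, and make the same correction in the third.

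The cost is a few sentences and one programming condition. No data change is needed, and the worst-case handling stays in place where the order really is unknown.

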#### Partial/Missing End Date

- If day is missing, then impute the last day of the month as in the table above unless the month is the same as the month of the last BATP visit date then impute the end date as the last BATP visit date.
- If month and day are missing, then impute as above to December 31 unless the year is the same as the last BATP visit date then assign imputed end date as the last BATP visit date.
- If the date is completely missing, check if AE/medication is ongoing before imputing a date and when the AE/medication started in relation to vaccination date. If the ongoing flag is missing, then assume that the AE/medication is still ongoing/medication is still being taken. In this case, do not impute the date. If the AE/medication stopped and the start date is prior to the last BATP visit date, then impute with the last BATP visit date. If the AE/medication started on or after the last BATP visit date, then impute an end date which is one day after the last BATP visit date.

These imputation methods will be used for assigning AEs to the vaccination period, and medications as prior/concomitant. Listings will display the original dates as captured in the eCRF.

#### **4.3.3 Assignment of AEs to Trial Phase**

Each AE will be assigned to the booster active trial phase (BATP) or booster follow-up (BFU) phase using date/time of vaccination and date/time of onset of the AE:

- All AEs starting at or after the booster vaccination but before the BEAP visit will be assigned to the booster active trial phase. For subjects who missed the BEAP visit, AEs within the booster vaccination + 28 day will also be assigned to the BATP.
- Any AEs starting after the booster vaccination but are not assigned to the BATP belong to the BFU period.

If onset time is missing and start date of AE coincides with the date of vaccination, the AE will be assigned to the BATP.

Each AE starting on or after the booster vaccination not matching the definition of a solicited AE is defined as an unsolicited AE. If a solicited AE begins outside of the 8-day period following the booster vaccination it will be considered an unsolicited AE regardless of the preferred term (PT). If start time of the AE is missing and start date coincides with date of vaccination, it will be

---

regarded as a treatment-emergent AE. If the start date is (partially) missing the AE will be regarded as a treatment-emergent AE following the worst-case principle.

Worst-case principle:

To avoid a potential misclassification of an AE to the BATP, if an imputed start date corresponds to the first of the month or to the first of the year, and matches the month and year of the booster vaccination date, then the AE will be assigned to the BATP. If the AE cannot be assigned to either phase because of a (partially) missing start date then it will be assigned to the BATP.

#### **4.3.4 General Considerations for AEs**

Medical Dictionary for Regulatory Activities (MedDRA) Version 19.1 will be used for coding of AEs.

Duration of an AE will be calculated as follows:

For Unsolicited AEs: expressed in [days]

- End date – start date of AE + 1 day. Note that duration can be calculated even if time of day is missing for either start or end dates, or if time is missing for both.
- In case of partially missing start date (month and/or day missing) or partially missing end date (month and/or day missing), duration will not be calculated.
- In case of an ongoing AE, the duration will not be calculated.

For Solicited AEs: expressed in [days]

- End date of AE – start date of AE + 1, where end date is the last day in which the symptom is defined as an AE, and start date is the first day in which the symptom is defined as an AE (disregarding if the AE occurred continuously between first and last day).
- In case of an ongoing AE, the duration will not be calculated.

Relative day of onset between vaccination and start of AE will be calculated as follows:

For Unsolicited AEs: expressed in [days]

- Start date of AE – booster vaccination date.
- In case of (partially) missing start date no calculation will be done.

For Solicited AEs: expressed in [days]

- The relative day is calculated as the day of first symptom intensity recording > 0.

---

- Start date of AE – booster vaccination date, where start date is the first day a symptom is defined as an AE; booster vaccination day corresponds to booster sub-study Day 0.

## 4.4 Analysis Variables

### 4.4.1 Demographic and other Baseline Characteristics

#### Demographics

- Age (years)
- Age Group ( $\geq 55$  to  $< 70$ ,  $\geq 70$ )
- Gender (male, female)
- Race (White/Caucasian, Black or African American, Asian, American Indian or Alaskan Native, Native Hawaiian or Other Pacific Islander, Other, Missing)
- Ethnicity (Hispanic or Latino, Not Hispanic or Latino, Missing)
- Height [cm]
- Body weight [kg]
- Body Mass Index (BMI)

#### Other baseline characteristics

- Medical history
- Prior and concomitant medications
- Pre-vaccination AEs

Age will be calculated based on date of informed consent for the booster sub-study. For weight and BMI, updated data will be obtained from the booster screening visit. Additional demographics and baseline characteristics will be obtained from the main study.

Demographics tables will be presented by treatment group for the BFAS and BIAS. Other baseline characteristics will be summarized by treatment group for the BFAS only.

Demographics and other baseline characteristics will be presented in separate subject listings.

### 4.4.2 Safety Variables

#### Physical examination (complete examination at Booster Screening Visit and targeted physical examination at BV1, BV2, BEAP, BFU1 and BFU2 Visits).

A targeted physical examination is guided by any signs or symptoms previously identified or any new symptoms that the subject has experienced since the last visit. A subgroup of subjects who are from the PBMC subset will have targeted physical examination at BV1b.

Only abnormal physical examinations will be listed.

Vital signs (at Booster Screening, BV1, BV2, BEAP, BFU1 and BFU2 Visits)

- Heart rate [beats per minute]
- Systolic and diastolic blood pressure [mmHg]
- Oral body temperature [°C]

The PBMC subgroup also has vital signs reported at BV1b.

Booster baseline, actual and change from booster baseline vital sign parameters will be summarized and individual subject listings will be presented.

12-lead electrocardiogram (ECG) data will not be collected for the booster sub-study.

Safety laboratory data (at Booster Screening Visit, BV2 and if clinically indicated at BFU1 or BFU2 Visits)

The safety laboratory measurements are performed at a central laboratory. Laboratory normal ranges are provided by the central laboratory.

Serum chemistry:

- Total Bilirubin (mg/dL)
- Alkaline Phosphatase (AP) (U/L)
- Aspartate Aminotransferase (AST) (U/L)
- Alanine Aminotransferase (ALT) (U/L)
- Creatinine (mg/dL)
- Sodium (mmol/L)
- Potassium (mmol/L)
- Calcium (mg/dL)

Hematology:

- Red blood cell count ( $\times 10^6/\mu\text{L}$ )
- Hemoglobin (g/dL)
- Total and differential White Blood Cell count (WBC) ( $\times 10^3/\mu\text{L}$ )
- Platelet count ( $\times 10^3/\mu\text{L}$ )
- Hematocrit (%)
- Mean corpuscular volume (MCV) (fL)
- Mean corpuscular hemoglobin (MCH) (pg)
- Mean corpuscular hemoglobin concentration (MCHC) (g/dL)
- Red blood cell distribution width (RDW) (%)

Booster baseline, actual values at each visit, and change from booster baseline safety laboratory parameters (serum chemistry and hematology) will be summarized and individual subject listings will be presented.

Shift tables will also be presented for serum chemistry and hematology using the categories of Missing, Below Lower Limit of Normal, Normal, and Above Upper Limit of Normal.

#### Pregnancy Test (BV1)

A urine  $\beta$ -human choriogonadotropin (HCG) pregnancy test will be conducted for all women of childbearing potential at BV1 prior to the booster vaccination. Pregnancy test results will be presented as individual subject listings.

#### Solicited local AEs reported in the subject memory aid (on day of booster vaccination and during the following 7 days)

- Injection Site Erythema (0 = 0, 1 denotes < 30 mm, 2 denotes  $\geq 30$  - < 100 mm, 3 denotes  $\geq 100$  mm)
- Injection Site Swelling (0 = 0, 1 denotes < 30 mm, 2 denotes  $\geq 30$  - < 100 mm, 3 denotes  $\geq 100$  mm)
- Injection Site Induration (0 = 0, 1 denotes < 30 mm, 2 denotes  $\geq 30$  - < 100 mm, 3 denotes  $\geq 100$  mm)
- Injection Site Pruritus (0 = Absent, 1 = Mild, 2 = Moderate, 3 = Severe)
- Injection Site Pain (0 = Absent, 1 = Painful to Touch, 2 = Painful when limb is moved, 3 = Spontaneously painful / prevents normal activity)

Solicited local AEs will be summarized by maximum intensity. Individual subject listings for solicited local AEs will also be presented.

